7.2.2.2. Immunogenicity

- Neutralizing antibody titers response to human Ad5 on day 0, 14, 28 and 168 (month 6).

7.3. Study Procedures

From beginning to the end of the study, there are 5 times visits of participants. The visit time, window period and visit content are shown in table 7-3-1 and 7-3-2.

Table.7-3-1 Visit plan for recombinant Ebola virus vaccine (Ad5-EBOV)

Visit	Visit time	Time window
Visit 0 (V0)	One day before the vaccination	—
Visit 1 (V1)	Vaccination at Day 0	—
Visit 2 (V2)	Day 14 after vaccination	±2 days
Visit 3 (V3)	Day 28 after vaccination	±3 days
Visit 4 (V4)	Day 168 (Month 6) after vaccination	±10 days

Table.7-3-2 Visit content and schedule for recombinant Ebola virus vaccine (Ad5-EBOV)

Content	V0	V1	V2	V3	V4
	Day	Day	Day	Day	Day
	-1	0	14	28	168
1 Collecting demographic information	☆				
2 HIV informed consent	☆				
3 Study Informed consent	☆				
4 Physical examination					

	Height, weight measurement		☆			
	Urine pregnancy tests (female)		☆			
	HIV antibody screening		☆			☆
5	Axillary temperature measurement		☆			
6	Inclusion and exclusion criteria for screening		☆			
7	Allocation of vaccine ID		☆			
8	Record on the Visit Record Form		☆			
9	Blood collection *:					
	Haematology and clinical chemistry tests ^		☆			
	Detection of anti-Zaire Ebola virus envelope glycoprotein antibody		☆	☆	☆	☆
	Detection of neutralizing antibodies to recombinant replication defective type 5 adenovirus		☆	☆	☆	☆
10	Vaccination		☆			
11	Observation for 60 minutes post-vaccination		☆			
12	Instruction on observation of solicited /unsolicited symptoms		☆			
13	Record of solicited / unsolicited symptoms post-vaccination		☆	☆	☆	
14	Report serious adverse events		☆	☆	☆	☆
15	Return of diary card		Return by safety follow-up staffs at day 8			

*Participants will be asked to donate 8ml blood (uncoagulation: 3ml, coagulation: 5ml) at the first visit, and 5 ml blood sample at the later visits. A total of 23 ml blood will be donated for each participant.

^ The toxicity grading panel for the haematology and clinical chemistry tests are provided in Appendix 13.

7.4. Sample size

We set the sample size as 250 people in high-dose vaccine group, 125 people in low-dose and placebo group, respectively. The sample size is 500 in total.

7.5. Criteria for pausing the study or an early termination

DSMB will review the reported safety data in the participants after vaccination. During the study

period, if an increase of risk for participants is noticed, the DSMB should promptly inform the principal investigator and sponsors. Sponsors, investigators and DSMB will have a panel meeting, and then DSMB will make final decision to pause or call an early termination of the study.

Administration of study injections and new enrollments will be paused, if:

- One serious adverse event may be associated with vaccination, or
- Incidence of new HIV infection post-vaccination reported in one (1) participant during 6 months after vaccination.

The study may come to an early termination, if:

- One fatal serious adverse event definitely associated to vaccination, or
- Incidence of new HIV infection reported in 1% (5 participants) during the 6 months post-vaccination, or
- Required by sponsor, or
- Required by regulatory authority, or

Required by institutional review board (IRB).

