9.4.6. Reporting of the occurrence of new HIV infection or pregnancy

The participants are asked to report new diagnosed HIV infection or pregnancy to the investigator or safety follow-up staffs. The report procedure shall follow the SAE report procedure and using SAE report form. The occurrence of new HIV infection also need to be reported to the DMSB for safety evaluation. Any pregnancy after vaccination during the study period will be monitored/followed up till delivery and 28 days after delivery of a normal baby. If delivery baby with abnormality, the cause of the abnormality will be investigated by the DSMB.

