9.5.3. Detection of HIV

9.5.3.1. Time point

HIV infection will be detected at day 0 and day 168 (month 6). Two drop of finger blood will be collected for each HIV test.

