9.7.6. Statistical Considerations for the DSMB

All the SAEs report along with the HIV infection report will be submitted to the DSMB. The DSMB will follow the SAE reports and determine the relationship with the vaccination of the investigational vaccines. If a SAE is considered to be “may be associated with vaccination”, or the reported incidence of new HIV infection is excess 2.5%, then the DSMB may unblind the reported cases, and re-estimate the risk of participants. If necessary, the DSMB discuss with sponsor and investigator about the risk of participants in this study which may resulting in a pause or an early termination of the trial. If a fatal SAE is considered “to be definitely associated with vaccination” or the reported incidence of new HIV infection is excess 5%, then the DSMB shall unblind the reported cases and call an early termination of the trial if necessary.

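### The HIV stopping limits contradict each other: section 7.5 and the synopsis act at 1 and 5 cases, section 9.7.6 only at 13 and 26 of 500

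*Protocol*

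**What the plan says.** Section 7.5, with the same text in the synopsis, sets two tiers.

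- **Pause.** "Administration of study injections and new enrollments will be paused, if" one serious adverse event may be vaccine-associated, or the HIV criterion is met: "Incidence of new HIV infection post-vaccination reported in one (1) participant during 6 months after vaccination". The pause is worded as mandatory.
- **Termination.** The study *may* end early after one fatal serious event definitely associated with vaccination, or on "Incidence of new HIV infection reported in 1% (5 participants) during the 6 months post-vaccination", or on request of the sponsor, regulator or review board.

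Section 9.7.6 also sets two tiers, for the DSMB.

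- **Lower.** A serious event that may be vaccine-associated, or: "the reported incidence of new HIV infection is excess 2.5%, then the DSMB may unblind the reported cases". The DSMB then re-estimates the risk and, if needed, holds a discussion that can end in a pause or early termination.
- **Upper.** A fatal serious event definitely associated with vaccination, or: "the reported incidence of new HIV infection is excess 5%, then the DSMB shall unblind the reported cases". The full action is that the DSMB "shall unblind the reported cases and call an early termination of the trial if necessary".

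After vaccination the only scheduled HIV test is at day 168 (section 9.5.3.1 and Table 7-3-2). Earlier cases depend on section 9.4.6: "The participants are asked to report new diagnosed HIV infection or pregnancy to the investigator or safety follow-up staffs". Section 9.5.3.2 plans to compare HIV incidence with the local rate and between vaccine and placebo.

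**The concern.** The protocol names HIV infection as a possible risk of this vector (section 12.3.1) and makes it a secondary safety endpoint (section 7.2.2.1). The amendment log gives participant safety and a requirement of the Pharmacy Board of Sierra Leone as the reasons for adding HIV to the pause and termination criteria.

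For that risk the protocol holds two sets of numbers. The tiers correspond, because the serious-event trigger is the same at each level in both sections. Only the HIV numbers differ, and by a wide margin. With 1 to 4 cases, 7.5 requires a pause. With 5 to 12 cases, its termination criterion is also met. In neither range is an HIV limit in 9.7.6 crossed. The DSMB, sponsor and investigators could each follow a written rule and disagree about what the same count requires.

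**Working it through.** **Inputs.** Total sample size 500 (section 7.4). HIV limits of 1 participant and 1% (5 participants) from 7.5 and the synopsis. HIV limits of more than 2.5% and more than 5% from 9.7.6. Assumed loss of 15% (section 9.7.1).

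**1. Reproduce the plan's own figure.** 0.01 × 500 = 5, as stated in 7.5. The protocol therefore counts on all 500.

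**2. Put 9.7.6 on the same base.** 0.025 × 500 = 12.5, exceeded from 13 cases. 0.05 × 500 = 25, exceeded from 26 cases.

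| Tier | 7.5 and synopsis | 9.7.6 |
|---|---|---|
| Pause / review | 1 case (0.2%) | 13 cases |
| Termination | 5 cases (1%) | 26 cases |

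**3. Can another denominator reconcile them?** Section 9.7.6 states none, so I tried the plausible ones.

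- 425 tested (500 × 0.85): 10.6 and 21.25, so 11 and 22 cases.
- 375 vaccinated (250 + 125): 9.4 and 18.75, so 10 and 19 cases.
- Annual rate over 500 × 168 / 365.25 = 230 person-years: 5.7 and 11.5, so 6 and 12 cases.

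No single denominator N can work. For 1 case to be the first count above 2.5%, N must be below 40. For 5 cases to be the first count above 5%, N must be at least 80 and below 100.

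**4. How likely is a count on which the sections differ?** The documents give no local HIV incidence, so the risks below are assumptions. The number of cases is taken as binomial with n = 500, the same risk in all arms and everyone assessed. For example, at 0.5%, P(at least 1) = 1 − 0.995^500 = 0.918 and P(at least 5) = 0.108, so P(1–4) = 0.810.

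| Assumed six-month risk | P(1–4) | P(5–12) | P(1–12) | P(13 or more) |
|---|---|---|---|---|
| 0.1% | 39% | 0.02% | 39% | about 0 |
| 0.25% | 70% | 0.9% | 71% | about 0 |
| 0.5% | 81% | 11% | 92% | about 0 |
| 1% | 43% | 56% | 99% | 0.2% |

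At a risk of 2%, 5 cases are reached with probability 97.2%, 13 cases with 20.7%, and 26 cases almost never.

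**5. What risk does each limit correspond to?** The true risk at which a limit is reached half the time is about 0.14% for 1 case (from 1 − 0.5^(1/500)), 0.93% for 5, 2.5% for 13 and 5.1% for 26. The two sections express very different tolerances for the same harm.

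**6. Does the amendment history settle it?** No. The log lists both the HIV criterion and section 9.7.6 as additions of the first amendment, so as far as it shows neither replaced the other.

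**The case against.** The strongest reply is that the sections are layered: 7.5 governs the conduct of the trial, and 9.7.6 governs when the DSMB unblinds. Terminating at the DSMB's discretion from 5 cases and being obliged to unblind above 5% can both be obeyed, and 9.7.6 does not forbid earlier action. Section 7.5 carries the title for pausing and termination, matches the synopsis, and lets the DSMB decide whenever increased risk is noticed. This reading does not remove the conflict. Section 9.7.6 itself names a pause or early termination as the outcome and attaches it to the same serious-event triggers.

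A second reply is that new HIV infections are reported on the SAE form (section 9.4.6), so one case judged possibly vaccine-related could reach the serious-event trigger in 9.7.6. But 9.7.6 lists HIV separately with its own percentages, which would then serve no purpose at the lower tier.

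Three points stand.

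- All reports go to the DSMB, so cases would not be missed.
- Dosing is a single day, and on my reading of the timetable (section 11, marked as for reference only) recruitment takes about one month. By day 168 a pause stops no injections. Before then it can act only on self-reported cases. The probabilities above count all cases through day 168, so they overstate the chance of a conflict while dosing can still be paused.
- Handling of day-168 cases is partly covered: the risk review in 9.7.6 has no time limit, and 9.5.3.2 plans the comparison with placebo. What is missing is a link between that comparison and the stopping criteria.

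**Conclusion.** The contradiction is real and should be corrected. For the same decisions the current text sets HIV limits of 1 and 5 cases in one place and, on 500 participants, 13 and 26 in another. The second set is 13 times the first at the lower tier and about 5 times at the upper (26 / 5 = 5.2). The counts 13 and 26 rest on a denominator of 500, which 9.7.6 does not state but 7.5 uses. Other plausible denominators narrow the gap without closing it.

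Counts from 1 to 12, where 7.5 is triggered and the HIV limits of 9.7.6 are not, have a probability of 39% to 99% at assumed risks of 0.1% to 1% with no vaccine effect. Those risks are illustrative. The contradiction itself does not depend on them.

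**What to change.** Set one HIV count for pause or review and one for termination. State the denominator and use the same *will* or *may* wording in the synopsis, 7.5 and 9.7.6. Agree the limits with the DSMB and with the Pharmacy Board of Sierra Leone. Unless they agree otherwise, replace 2.5% and 5% in 9.7.6 with the limits of 7.5: 1 participant, and 1% (5 participants).

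That discussion should recognise that a limit of one case will often be reached by background infection alone (39% to 99% at the assumed risks). Unblinding at the lower tier should therefore remain discretionary, as 9.7.6 now has it.

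Add one sentence on cases found at day 168: the DSMB reviews them by arm against placebo, using the comparison in 9.5.3.2.

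The cost is a protocol amendment, matching DSMB wording, and regulator and ethics agreement. No visits or tests are added.

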7.6. Duration of study

The whole follow-up period for each participant will be 6 months.

8. PARTICIPANTS

8.1. Participants selection

Healthy local 18-50 years old residents in Sierra Leone will be informed by ethical review committee approved consent to be a volunteer. After physical examination and screening according to the following inclusion and exclusion criteria, they will be eligible to participate in this study. Any employee who carried out the research, the relevant researchers, and the contract research organization (CRO) could not be the participants. Following inclusion and exclusion criteria will be used to select the eligible participants for this study.

8.2. Inclusion criteria

- Aged between 18 and 50 years

- Able to understand the content of informed consent and signed the informed consent
- Able and willing to complete all the secluded study process during the whole study follow-up period (about 6 months).
- Negative in HIV diagnostic blood test on day of enrollment
- Axillary temperature $\leq 37.0^{\circ}$ C on the day of enrollment
- Non-pregnant females with a negative result in the urine pregnancy test on day of enrollment
- General good health as established by medical history and physical examination.

8.3. Exclusion criteria

- Infected by Ebola virus
- Vaccination with other Ebola vaccine
- HIV infection or other serious immunodeficiency disease
- Allergic history of any vaccination or drugs, or allergic to any ingredient of the Ad5-EBOV, such as mannitol
- Family history of brain or mental disease
- Woman who is pregnant or breast-feeding
- Any acute fever disease or infections in last 7 days
- Major congenital defects or not well-controlled chronic illness
- Asplenia or functional asplenia
- Platelet disorder or other bleeding disorder
- Faint at the sight of blood or needles.
- Prior administration of immunodepressant or corticosteroids, antianaphylaxis treatment, cytotoxic treatment in last 6 months
- Prior administration of other research medicines in last 1 month
- Prior administration of attenuated vaccine(s) in the last one month
- Prior administration of inactivated vaccine(s) in the last 14 days
- Any condition that in the opinion of the investigators may interfere with the participants' compliance or evaluation of study objectives

8.4. Withdraw from the study

The participants have the right to withdraw from the study at any time during the study period, and the investigator should record and handle the following cases:

- Before the termination because of loss of contact.
- Request from participants without any reasons.
- Reasons unrelated to the study requirements should be recorded for the withdrawal such as go out for a long time, moved.
- Reasons related to the study requirements should be recorded, such as the inability to tolerate the adverse reactions, endure biological specimen collection. AE/SAE should be solved by investigator.
- Early termination of the study can be advocated by participants, including stopping vaccination, biological samples acquisition and safety otherwise data before withdrawal can be used to analysis. If the participants banned the investigators to continue using all the relevant research issues, the research information will not be used for analysis.
- Part of early termination of the study can be advocated by participants such as stopping vaccination, biological samples acquisition while other researches continue.

8.5. Termination of study

8.5.1. Completed safety observation

Safety of 28 days after immunization and the SAE reports in entire study period are completed.

8.5.2. Completed immunogenicity research

The participants meet the inclusion and exclusion criteria participated in randomization, vaccination, processing the blood collection at day 0, 14, 28 and 168 (month 6).

9. METHODS AND PROCEDURES

9.1. Participants screening

Healthy local 18-50 years old residents in Sierra Leone will be informed about the study and approved consent sought from them to be a volunteer. After physical examination and screening according to the inclusion and exclusion criteria, they will be eligible to participate in this study. Before they sign the informed consent, they have enough time to think about it, and a withdrawn at any time during the trial is permitted.

Following operation will be performed during the selection:

- Demographic data.
- Physical examination, including HIV test and urine pregnancy test (female only).
- History of disease.
- Conforming to the inclusion criteria and not the exclusion criteria.

9.1.1. Laboratory examination

9.1.1.1. Urine pregnancy test

Pregnancy test will be performed on target women of childbearing age (18-50 years old) for early pregnancy detection.

9.1.1.2. HIV antibody screening

HIV antibody will be screened for all the volunteers. Only the HIV specific antibody negative volunteers could be enrolled in the group.

9.2. Randomization and Blinding

9.2.1. Randomization and blinding method

Randomization list will be generated by independent statistician using SAS software. The independent statistician will generate the randomization list of 500 random codes, randomly allocated these codes to the high dose vaccine, or low dose vaccine, or placebo in a ratio of 2:1:1, using a “Proc plan” procedure in SAS by block randomization. Each person dose of investigational vaccines is assigned

a code from a randomization list. The package of the investigational vaccine (including high dose vaccine, low dose vaccine and placebo) will be relabeled, using identical package with a randomized code which is the unique identifier for each person dose. Therefore, all the vaccine and placebo doses are blindly coded. The persons who participate in randomization and blinding must not participate in any other process of the clinical trial, also must not disclose the contents of blinding to any personnel. Eligible participants enrolled into this study, will be assigned a sequential number according to their sequence of enrolment and received vaccine or placebo labelled with the same numbers. Thus, participants are randomly assigned to receive high dose vaccine, or low dose vaccine, or placebo in a ratio of 2:1:1.

The independent statistician should produce a copy of emergency blinding code which should note the title of program and the character “To Be Opened Only in Case of Emergency”. Personnel who involved in randomization and blinding are not allowed to participate in any other procedure in this study.

Blinding will be maintained for all participants and investigators and their study staff participating in this study.

9.2.2. Method of blind breaking and unblinding

When the last participant completed the 28 day visit, CRF completion, a database entry and blind state audit should be completed. Un-blinding should be after the publication database lock statement when all parties involved in such as the sponsor, investigator, statistical representatives.

During the study, the breaking of the treatment code is forbidden, except in the event of a medical emergency when the investigator believes it is necessary to determine the treatment code in order to initiate appropriate treatment. If knowledge of the treatment code is required, the investigator will open only the specific participant’s code envelope. A signature, date, time and reason will be written on the opened code envelope and the participant with this code has to be withdrawn from this study.

The investigator will assess the relationship between the adverse event and the investigational products before the treatment code is un-blinded. The investigator will immediately notify the sponsors at the 24 hours emergency call number ([name] [name]) when the treatment code blinding is broken on any participant for any reason during the study. The reason for the blinding being broken

must also be documented in the participant's medical records and in the CRF.

At the end of the study, all code envelopes (intact and opened) must be accounted for and are to be collected by the monitor to be destroyed.

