7.2.2. Secondary endpoints

7.2.2.1. Safety

- Occurrence of unsolicited adverse reactions within 28 days after vaccination.
- Occurrence of serious adverse reaction during the whole follow-up period (6 months).
- Post-vaccination Rate of infected with HIV.

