9.3.2. Administration

One injection will be allocated intramuscularly in the arm at day 0.

Experimental vaccine group A (4×10^{10} vp/vial, 4 vials): 1 ml sterilization injection water per dose to dilute 2 vials (4×10^{10} vp/vial), one shot in each arm, total dose of 1.6×10^{11} vp. The inoculation site was the central lateral deltoid in the upper arm, and inoculation route was intramuscular injection

Experimental vaccine group B (4×10^{10} vp/vial, 2 vials): 1 ml sterilization injection water per dose to dilute 1 vial (4×10^{10} vp/vial), total dose of 8×10^{10} vp, one shot in each arm. The inoculation site was the central lateral deltoid in the upper arm, and inoculation route was intramuscular injection

Placebo group (0 vp/ vial, 2 vials): 1 ml sterilization injection water per dose to dilute 1 vial, total dose of 0 vp. The inoculation site was the central lateral deltoid in the upper arm, and inoculation route was intramuscular injection

Before injection, 75% alcohol is used for disinfection at the injection site and intramuscular vaccination will be administrated several minutes later. Shaking the vaccine before use and make vaccine fully dissolved in sterile water for injection. No intravascular, intradermal or subcutaneous injection is allowed with the investigational vaccine. During the vaccination and 60-minute safety surveillance after vaccination, appropriate emergency medical equipment and doctors should put on standby in case that possible allergic reaction after injection.

Only the qualified doctors, Community Health Officer (CHO) or qualified nurse will give the injection. For the purpose of vaccine/placebo administration, a medically qualified member of the study staff is a study physician or a study nurse, as applicable to the investigator's local practice.

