9.7.4. Analyzed data sets definition

9.7.4.1. Data set for safety evaluation

All randomized participants who received vaccination should be included in the safety evaluation. Thus, the safety analysis will be performed on the basis of (Intention-To-Treat) ITT cohort. Events will be reported on per-individual basis, i.e. counting individuals rather than events. This means that even if a participant suffered a same event repeatedly during the follow-up, the event will be counted only once, except for SAEs. Repeated same adverse events in participant will be summarized according to the following rule: if a participant suffered the same adverse event more than once, the event will be assigned the worst severity, the closest relationship to the vaccination and the earliest starting date. In the listings, however, all occurrences of the adverse events will be shown.

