9.7.4.2. Data set for immunogenicity evaluation

Full analysis set (FAS) for immunogenicity analysis: FAS is based on ITT (intention to treat analysis) principle to determine the participants. All of the participants that meet the inclusion / exclusion criteria, randomization, receiving vaccination, and have at least one blood testing result after vaccination ,were included in the FAS set for immunogenicity.

Per-protocol set (PPS): It is a subset of FAS. In this set, all participants that meet the inclusion / exclusion criteria and complete the vaccine inoculation within visit window according to the protocol, and complete the blood collection on day 0, 14 and 28, with no significant deviation or violation of protocol.

In this study, the FAS are the primary analysis set for immunogenicity evaluation, but the PPS will also be analyzed at the same time. Any difference of analysis results existed between PPS and FAS, will be discussed in the report.

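### A participant whose code is broken in an emergency must be withdrawn, which ends observation after a single-day vaccination and loses later safety, HIV and antibody data for a small group selected by a severe event

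*Protocol*

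**What the plan says.** Protocol section 9.2.2 forbids breaking the treatment code "except in the event of a medical emergency when the investigator believes it is necessary to determine the treatment code" so that treatment can begin. The investigator opens that one envelope, documents it, and "the participant with this code has to be withdrawn from this study". No exception is given.

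Other sections that bear on this rule:
- Section 8.4 describes early termination at the participant's wish as stopping vaccination, "biological samples acquisition and safety otherwise data before withdrawal can be used to analysis". It also allows a partial termination, again at the participant's wish. A code break is not among its listed cases.
- Section 9.3.2: "One injection will be allocated intramuscularly in the arm at day 0". No later study dose is planned.
- Section 7.2.2.1 sets as a secondary endpoint: "Occurrence of serious adverse reaction during the whole follow-up period (6 months"). It also lists post-vaccination HIV infection.
- Section 9.5.3.1: "HIV infection will be detected at day 0 and day 168 (month 6").
- Section 9.7.4.1: "All randomized participants who received vaccination should be included in the safety evaluation".
- Section 9.7.4.2 admits to the FAS only eligible, randomized and vaccinated participants who "have at least one blood testing result after vaccination".

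**The concern.** In a trial with repeated dosing, withdrawal after a code break might be defended as a way of stopping study treatment. Here there is none left to stop once day 0 is over, so the only thing that withdrawal can end is observation.

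The loss is also not random. A participant leaves under this rule because of a medical emergency, so missingness depends on a safety outcome. The 15% loss allowance in section 9.7.1 makes up numbers; it does not correct for selective loss.

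At stake, for each such participant, are later serious events up to month 6, the only scheduled HIV test after vaccination, and the antibody samples not yet drawn. HIV follow-up has a stated safety purpose: section 12.3.1 says the vector may raise HIV risk and undertakes to follow participants closely for six months. Section 7.5 acts on as few as one new infection, so single cases count.

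**Working it through.** The plan states no figure on this point, so the check is mainly a reading of the sections together.

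**1. Who is withdrawn?** Only participants whose code the investigator opens in an emergency (9.2.2). A participant with a serious adverse event (SAE) but no code break stays in. The DSMB may also unblind reported cases (9.7.6), and no withdrawal rule is attached there.

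**2. What does withdrawal end?** Section 9.2.2 does not define it. The nearest definition is full early termination in 8.4: sampling and safety collection stop, and earlier data remain usable. No section keeps a participant withdrawn for a code break in the scheduled visits.

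**3. What is kept?** The participant and the event already recorded stay in the safety set (9.7.4.1). Section 9.4.7 requires an SAE to be treated and documented until it resolves or stabilizes. Section 9.4.5 requires every SAE during the study to be reported.

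**4. What is lost, by time of the code break?**

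| Code broken | Scheduled samples lost | HIV test lost | FAS |
|---|---|---|---|
| Before Visit 2 (day 14) | Days 14, 28, 168 | Day 168 | Out: no post-vaccination result |
| Between Visits 2 and 3 | Days 28, 168 | Day 168 | In if the day-14 result exists |
| After Visit 3 | Day 168 | Day 168 | In if an earlier result exists |

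In every row, scheduled safety assessment up to month 6 is lost as well.

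**5. Does withdrawal protect the blind?** Section 9.2.3 opens the data after the day-28 lock and continues follow-up to month 6, so the plan already accepts follow-up with the allocation known. It also keeps laboratory staff blinded throughout, so one opened envelope does not expose the antibody assays.

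**6. Size.** The plan gives neither the number of code breaks nor the risk of later events. Let k participants be withdrawn under the rule, each with risk q of a later serious event or HIV infection. The chance that at least one such event goes unobserved is 1 − (1 − q)^k. Both k and q are assumptions:
- k = 1: q = 0.1 gives 1 − 0.9 = 10%; q = 0.3 gives 1 − 0.7 = 30%.
- k = 5: q = 0.1 gives 1 − 0.9^5 = 41%; q = 0.3 gives 1 − 0.7^5 = 83%.

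These show how the loss scales and are not forecasts.

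**7. Power is not the issue.** Take the 9.7.1 positive rates of 85% (low dose) and 95% (high dose), two-sided α 0.05, no continuity correction. The power is Φ{[0.10 − 1.96·√(p̄(1 − p̄)(1/n₁ + 1/n₂))] / √(0.85·0.15/n₁ + 0.95·0.05/n₂)}, with p̄ the pooled rate.
- n₁ = 125, n₂ = 250: (0.10 − 0.0593)/0.0348 = 1.169, power 87.9%.
- n₁ = 120, n₂ = 250 (five low-dose participants lost): (0.10 − 0.0599)/0.0354 = 1.134, power 87.2%.

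**The case against.** The best case for leaving the rule alone is that it will hardly ever operate. The Jiangsu phase I trial recorded no SAEs in 120 participants over 28 days (4.2), and the Hangzhou trial no serious adverse reaction in 61. An emergency in which the code is needed for treatment is rarer still. If the blind opens after the day-28 lock, the rule matters mainly for the first month. Safety analysis is mainly descriptive, and active collection of adverse events stops after day 7 for everyone (9.4.1). Suspected unexpected serious reactions reported after a participant has completed the trial still qualify for expedited reporting (9.4.5). Section 8.4 recognises partial termination, so one may argue that the extent of withdrawal is merely undefined.

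Much of this stands, and it keeps the point small. It does not rescue the rule. Visits 2 to 4 still include safety assessment and blood sampling, and Visit 4 the HIV test, and a withdrawn participant has none of them. Partial termination in 8.4 is at the participant's own wish, and 9.2.2 does not invoke it. The day-28 limit is itself unsettled: 9.2.3 opens the month-6 visit, whereas 9.7.2 says the sites remain blinded. If the sites do stay blinded, the rule operates to month 6.

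A reader might go further and infer the following, none of which the protocol supports:
- *All participants with serious events are dropped.* Only those whose code the investigator opens are.
- *The emergency itself goes missing.* Sections 9.4.5, 9.4.7 and 9.7.4.1 keep it.
- *The rule contradicts the safety set.* That set is defined by randomization and vaccination, and withdrawal does not change membership. Later observation is incomplete, but no one leaves the set.
- *The bias favours the high dose.* Solicited reactions in Jiangsu did rise with dose (19, 27 and 36 participants in the placebo, low-dose and high-dose groups), but there were no SAEs from which to infer a dose gradient in emergencies.

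**Conclusion.** The point holds as a poor design choice with a small expected effect. The rule is explicit and mandatory, stops no study treatment, and makes loss to follow-up depend on a severe event. It runs against the six-month SAE and HIV endpoints and, for a code break before the first post-vaccination sample, against inclusion in the primary immunogenicity set.

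The number affected is likely very small, possibly none, and power is essentially untouched. The direction of any bias is unknown, and the documents allow no estimate of the share of SAE cases affected.

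The conclusion rests on one reading: that withdrawal in 9.2.2 has the meaning of full early termination in 8.4. If the sponsor intended something narrower, the protocol does not say so, and the same correction is needed.

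**What to change.** Replace the withdrawal sentence in 9.2.2 with a statement along these lines: breaking the code does not by itself end data collection. The participant continues safety follow-up, scheduled blood samples and the HIV test to day 168 unless consent is withdrawn. The participant stays in the safety set, and in the FAS where its conditions are met. The code break is documented, and any exclusion applies at most to the PPS.

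Bring 7.2.2.1, 8.4, 9.7.4.1 and 9.7.4.2 into line with this, and reconcile 9.2.3 with 9.7.2 on whether the sites are blinded after day 28. When the code may be opened, and how the emergency is treated, need not change.

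The cost is about one sentence plus cross-references, with no procedures beyond those already scheduled. The small downside is that site staff who know the allocation will follow these few participants. Laboratory staff remain blinded under 9.2.3, and the documented code breaks let the report identify the participants concerned.
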